# 2. DATA

A summary of the participant assessments and data collection is described in the table below.

	Baseline Visit	Time of	1 month	6 months	1 year	Annual Telephone
	(Hospital Visit	Procedure*	(Hospital	(Telephone	(Hospital	Follow-up from Year 2
	1)	(Hospital Visit 2)	Visit 3)	Follow-up Call)	Visit 4)	until Trial End
Informed Consent	V					
Patient Diary	V					
Entry Form +	V					
Imaging Form	V				V	
Stenting Form		V				
Follow-up Forms‡			v	V	V	V
Cross-Over Form		V	v	V	V	V
Endpoint Form			v	v	v	V
Adverse Event Form		V	v	v	V	V
Death Report Form		V	V	V	V	V

\*If allocated angioplasty/stenting.

+Baseline data, including patient details, cerebral events (presenting and past events), risk factors, medication prior to trial entry, modified Rankin at time of randomisation, quality of life form completed, imaging prior to randomisation, and final screening prior to randomisation.

‡Follow-up forms include details on events since last follow-up, modified Rankin at time of follow-up, quality of life form completed, risk factors, medications at follow-up, and procedures performed since randomisation.

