# 3.3. Comparison of treatment strategies

See Table 2 below for a proposed presentation of primary and secondary endpoints.

Main analyses will be performed on an intention-to-treat (ITT) basis, with inclusion of all randomised patients in the analysis according to the treatment group they were initially allocated. Analyses will also be done per-protocol (PP), including participants who met the inclusion criteria and received the assigned treatment. During trial monitoring is has become apparent that, for some cases, vertebral stenosis of at least 50% has not been confirmed on central imaging review.

The per-protocol analysis will include:

- 1. Patients with symptomatic vertebral stenosis from presumed atheromatous disease
- 2. Patients in whom central imaging review confirmed vertebral stenosis of ≥50%
- 3. Patients who received the allocated treatment

ITT and PP analyses will be performed for the primary and secondary endpoints, which are listed below. Not all secondary endpoints may be reported in the published article but the following analyses will be presented in the study plan;

Primary endpoint:

• Fatal and non-fatal stroke in any arterial territory during trial follow-up

Secondary endpoints:

- Fatal or non-fatal stroke in any arterial territory at 3 months post-randomisation
- Posterior circulation stroke (including periprocedural stroke) during follow-up
- Periprocedural stroke or death (within 30 days of procedure)
- Posterior circulation stroke and TIA during follow-up
- Any disabling stroke (defined by a Modified Rankin score ≥3) during follow-up
- Death of any cause during follow-up
- Restenosis (stenosis >50% in the treated artery) in treated artery during follow-up
- NHS and personal social services costs (UK patients only)\*
- Quality-adjusted life years\*
- Within-trial and long-run incremental cost-effectiveness\*

\*As specified in the protocol (pages 12-13).

The main analyses will be repeated for intracranial and extracranial strokes separately.

The intensity of medical treatment will be compared between the two groups over the first 30 days and over the full trial duration by assessing presence/absence and number of the following treatments: anti-platelets; statins; antihypertensives. Blood pressure measurements during follow-up in the two groups will be compared. Treatment of diabetes mellitus and current smoking will be recorded.

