# 4. PROPOSED TABLES AND FIGURE LEGENDS

Table 1. Baseline characteristics of patients enrolled into the VIST, according to treatment group (intention-to-treat population) (per protocol data will be presented in columns to the right or in a separate similar table)

Characteristic a	Best medical treatment	Angioplasty/stenting	P value b
	group (n = xx)	group (n = xx)	
Age (years)			
Male, n (%)			
Body mass index c			
Vascular risk factors			
Treated hypertension			
Treated hyperlipidaemia			
Previous myocardial infarction			
Angina in last 6 months			
Peripheral artery disease			
Atrial fibrillation			
Qualifying event			
TIA			
Non-disabling stroke d			
Location of vertebral artery target			
stenosis			
Extracranial (V1 to V3)			
Intracranial (V4)			
Modified Rankin Score			

TIA, transient ischemic attack; VIST, Vertebral artery Ischaemia Stenting Trial.

a Values are number (%) of patients or mean (± SD).

b Treatment groups are compared using Fisher's exact test or *t* tests.

c BMI is calculated as weight (kg) divided by height (m) squared.

d Modified Rankin scale score  $\leq$ 3 at inclusion.

Table 2. Medica	l treatment and b	ood pressure	and risk factor	control over th	ne first 30 days over

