# the whole study follow-up

	Best medical treatment group (n = xx)		Angioplasty/stenting group (n = xx)		
	First 30 days	Whole follow-up a	First 30 days	Whole follow-up a	
Antiplatelet medication					
Aspirin alone					
Clopidogrel alone					
Aspirin and clopidogrel					
Other					
Oral anticoagulants					
Statin therapy					
Antihypertensive medication					
Blood pressure b					
Systolic (mmHg)					
Diastolic (mmHg)					
Treated diabetes mellitus					
Non-insulin dependent					
Insulin dependent					
Current smoking					
a Where treatments ch	anged during follo	w-up the treatment give	n for the majority	of follow-up is	

recorded.

b Blood pressure measurements were only recorded at clinic follow-ups at 3 months and 1 year.

Table 3. Primary and secondary endpoint events during follow-upa (intention-to-treat population) (per-protocol data will be presented in columns to the right or in a separate similar table)

	No. (%) of patients/person-months			
	Best medical treatment	Angioplasty/stenting	HR (95% CI)	P value
	group (n = xx)	group (n = xx)		
Primary endpoint				
Fatal or non-fatal stroke in any arterial territory b				
Extracranial vertebral artery target stenosis				
Intracranial vertebral artery target stenosis				
Secondary endpoints				
Fatal or non-fatal stroke in any arterial territory b at 3 months				
Posterior circulation stroke b				
Periprocedural stroke or death				
Posterior circulation stroke or TIA				
Death from any cause				
CI, confidence interval; HR, hazard ratio; mRS, modified Rankin S	cale; TIA, transient ischemic	attack.		

a Complete follow-up (≥1 year) if not otherwise indicated.

b Including periprocedural (30 days post-procedure) stroke.

	No. (%) of			
	Best medical treatment	Angioplasty/stenting	OR (95% CI)	P value
	group (n = xx)	group (n = xx)		
Cerebrovascular event				
Fatal or non-fatal stroke				
Posterior circulation stroke				
Extracranial				
Intracranial				
Posterior circulation stroke or TIA				
Any disabling stroke (mRS score ≥3)				
Major operation related SAEs				
Death from any cause				

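### A Rankin score of 3 is non-disabling at entry but disabling as an outcome, and no worsening is required, so a minor stroke in a patient still at 3 counts as disabling

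*SAP*

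**What the plan says.** Three places in the SAP attach a modified Rankin (mRS) cut-off to the words disabling or non-disabling.

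- Section 3.3, secondary endpoints: "Any disabling stroke (defined by a Modified Rankin score ≥3) during follow-up".
- Section 4, Table 4 (events within the first 30 days, analysed as odds ratios): "Any disabling stroke (mRS score ≥3", the same threshold.
- Section 4, Table 1, footnote d, attached to the qualifying-event row for non-disabling stroke: "Modified Rankin scale score $\leq$ 3 at inclusion".

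Section 2 shows that the scale is scored repeatedly. The entry form holds "modified Rankin at time of randomisation" and the follow-up forms hold "modified Rankin at time of follow-up". The SAP does not say which post-stroke reading decides whether a stroke was disabling. It does not refer to the patient's score before the stroke, and it has no rule for patients who enter at 3.

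**The concern.** The outcome rule is an absolute threshold, applied to a population that the SAP itself describes as possibly already at that threshold. Entrants at 0, 1 or 2 must lose function to reach the endpoint. An entrant at 3 who has not improved needs only to have a stroke of any severity.

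The endpoint is meant to separate severe from minor strokes. If some events qualify because of disability that existed before randomisation, it partly measures who was disabled at entry. Three consequences follow.

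- If the misclassified strokes fall similarly in both arms, they tend to dilute a real difference in disabling stroke. Section 1 says the trial is treated analytically as non-inferiority or equivalence, and under that framing a pull towards no difference is not conservative.
- With 182 patients enrolled (Section 3.5), a chance imbalance in the number entering at 3 can carry into the endpoint through those who later have a stroke.
- The same rule feeds the 30-day comparison that Section 3.3 uses to judge operative risk, where there has been little time to recover from a score of 3.

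**Working it through.** **Step 1: the definitions side by side.** The SAP states no figure for this endpoint, so there is none to reproduce. The check is on the definitions, over the scale 0 to 6.

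| Score before a new stroke | Label if the qualifying event was a stroke (footnote d) | Worsening needed to meet the outcome rule (≥3) |
|---|---|---|
| 0 | non-disabling | 3 points |
| 1 | non-disabling | 2 points |
| 2 | non-disabling | 1 point |
| 3 | non-disabling | none |

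The scores satisfying both ≤3 and ≥3 reduce to a single value, 3.

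**Step 2: does anything else in the SAP remove the overlap?** The planned adjustment (Section 3.3) covers centre, age, sex, body mass index and the vascular factors of Table 1. The Rankin score is a separate row of Table 1, outside the vascular factors, so it is not a covariate. The adjustment is also an additional analysis, conditional on event numbers. No text requires a change from baseline.

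**Step 3: illustrative size.** The document gives neither the share entering at 3 nor the share of strokes that are disabling, so both are assumptions.

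- Strokes: apply the 3-year risks of Section 3.5 to the 182 enrolled, assuming equal arms. Control risk 24%; stented risk 24% × (1 − 0.45) = 13.2%. Then 91 × 0.24 + 91 × 0.132 = 21.8 + 12.0 = 33.9, about 34.
- Share of entrants at 3: 5–15% (assumed), with the same stroke risk as other entrants.
- Share of strokes truly disabling: one third (assumed), so 34 / 3 ≈ 11.

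Strokes in entrants at 3:

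- 34 × 0.05 = 1.7
- 34 × 0.15 = 5.1

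One third of these are truly disabling and already among the 11. Only the other two thirds are spurious:

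- 1.7 × 2/3 = 1.1; 1.1 / 11 = 10%
- 5.1 × 2/3 = 3.4; 3.4 / 11 = 31%

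This is an upper bound for the given assumptions, because it supposes that nobody at 3 recovers before the new stroke. If no patient entered at 3, the excess is zero.

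**The case against.** The strongest reply is that the two texts do different jobs. Footnote d labels a category in a baseline table, while the outcome rule is the same in both places where it appears, so the endpoint taken alone is consistent. An absolute threshold is also simple and reproducible, and the protocol, to which Section 1 defers for details, may define the terms. This stands in part: nothing here shows that the endpoint is applied inconsistently. It does not remove the conflict, since one SAP gives the same score opposite labels. Nor does reproducibility help where the rule reproducibly counts a stroke that left the patient no worse. If footnote d is merely a slip for a score below 3, it still needs correcting.

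A reader might infer that every new stroke in a patient who entered at 3 is automatically disabling. The SAP does not support that. The score is taken again at follow-up, follow-up runs from 1 to about 7.5 years, and a patient who improved to 2 or below and then has a minor stroke is not counted. The point is limited to patients still at 3 when the new stroke is scored.

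A reader might also divide all strokes in entrants at 3 by the 11 truly disabling ones and get 1.7 / 11 = 15% to 5.1 / 11 = 46%. That counts the truly disabling strokes among them twice.

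Two further objections hold. Table 1 shows the Rankin score by arm, so an imbalance at entry would be visible. And a rule comparing with the last recorded score can err the other way: a patient at 3 at randomisation who recovers to 1 and then has an early stroke that returns the score to 3 would be left out, although that stroke was disabling. The fix has to allow for this.

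**Conclusion.** The definitional conflict is certain on the SAP's own text. Followed as written, the outcome rule misclassifies a minor stroke in a patient who entered at 3 and remains there. This affects one of the ten listed secondary endpoints and one row of the 30-day table. The primary endpoint, stroke of any severity, is untouched.

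The size is not known. The bound of about 1.1–3.4 spurious events rests on the assumed inputs listed in the working and should not be quoted as an estimate for this trial. The SAP does not show that anyone entered at 3. The point is worth correcting because the endpoint will have few events and the repair needs little more than wording, not because a large distortion has been shown.

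**What to change.** Before unblinding:

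1. Reconcile footnote d of Table 1 with Section 3.3 and Table 4, so that one cut-off separates disabling from non-disabling throughout.
2. Define a disabling stroke as one followed by an mRS of at least 3 that is also at least one point above the patient's score immediately before that stroke. Take the pre-stroke score from the endpoint form where it is available there, otherwise use the last recorded score. The SAP does not list that form's fields, so this needs checking.
3. State the time after the stroke at which the deciding score is read.
4. Report the count under the absolute rule (mRS of at least 3) as a sensitivity analysis. The last recorded score may be out of date, especially in the first 30 days, when the randomisation score may be the only one, and between annual calls.

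The cost is SAP wording and a reclassification of stroke events while still blinded; Rankin scores are already collected at entry and follow-up. The downside is that a few events move out of the endpoint and some may be misclassified where the pre-stroke score is old. The sensitivity analysis shows how much that matters.

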In analyses of primary and secondary endpoint events at 3 months post-randomisation and during complete follow-up, follow-up will start immediately after randomisation. Follow-up will range from 1 year for the last recruited patients to about 7.5 years for first recruited patients. If the event numbers are sufficient, hazard ratios with 95% confidence intervals will be estimated by using Cox proportional hazards regression models, with patients censored at the time of first event of each type, death, last contact date, or the end of follow-up. The proportional hazards assumption for the treatment will be tested using Schoenfeld residuals. Kaplan-Meier survival analysis will be used to construct time-to-event curves, and the log-rank test will be used to evaluate whether there is a statistical significance difference in the cumulative risk of stroke between the two treatment groups.

We will also analyse short term outcomes to assess the operative risk. For this we have chosen a 30 day follow-up period but this may be adjusted before unblinding to results and analysis if we find stenting has not been carried out by 30 days in a significant number of individuals. For 30-days events, follow-up for each patient will start immediately after recruitment for patients allocated medical treatment alone and immediately after the stenting procedure for patients allocated stenting. If stenting was not performed in a patient allocated stenting, follow-up will begin directly after randomisation. The proportions of outcome events within 30-days of treatment will be compared with exact logistic regression to estimate odds ratios and 95% confidence intervals.

In additional analyses, provided that the event numbers are sufficient, we will adjust for centre and predefined risk factors (i.e., age, sex, body mass index and the vascular factors presented in Table 1). Hypothesis tests will be 2-sided using a significance level of 0.05. Statistical analysis will be performed using Stata (StataCorp, College Station, TX).

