# Table 4. Serious adverse events within the first 30 days (intention-to-treat population)

CI, confidence interval; mRS, modified Rankin Scale; OR, odds ratio; TIA, transient ischemic attack.

ANALYSIS OF ANGIOGRAPHIC IMAGING DURING					
STENTING					
	Pre-Stenting	Immediate post-stenting			
Angiographic stenosis	? mean (SD)	? mean (SD)			
REPEAT NON-INVASIVE IMAGING AT 1 YEAR					
	At randomisation	At 1 year			
No. (%) with stenosis ≥50%					
Angioplasty/stenting					
Best medical therapy					
REPEAT NON-INVASIVE IMAGING AT 1 YEAR No. (%) with stenosis ≥50% Angioplasty/stenting Best medical therapy	At randomisation	At 1 year			

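### Restenosis of the treated artery falls under ITT, per-protocol and time-to-event rules that do not fit it, and its threshold differs from that of the only table that could report it

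*SAP*

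**What the plan says.** **Endpoint.** SAP section 3.3 lists "Restenosis (stenosis >50% in the treated artery) in treated artery during follow-up" among the secondary endpoints.

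**Analysis sets.** The same section states "ITT and PP analyses will be performed for the primary and secondary endpoints, which are listed below". ITT is described as analysis "with inclusion of all randomised patients in the analysis according to the treatment group they were initially allocated". The per-protocol set is limited to patients with presumed atheromatous symptomatic stenosis, confirmed centrally at 50% or more, who received their allocated treatment.

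**Clock and model.** Section 3.3 also says "In analyses of primary and secondary endpoint events at 3 months post-randomisation and during complete follow-up, follow-up will start immediately after randomisation". Follow-up runs from 1 year to about 7.5 years. Cox regression is to be used if there are enough events, with censoring at first event, death, last contact or end of follow-up. No separate rule is given for restenosis.

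**Imaging schedule.** The table in section 2 marks the Imaging Form at baseline and at 1 year only. From year 2, scheduled contact is under the column headed "Annual Telephone" follow-up.

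**Table shells.** Table 3 in section 4, which carries the hazard ratios, has no restenosis row. The imaging table printed after Table 4 has a block headed "REPEAT NON-INVASIVE IMAGING AT 1 YEAR", which gives "No. (%) with stenosis ≥50" per cent for each arm, at randomisation and at 1 year. Its other block gives angiographic stenosis before and immediately after stenting, as mean (SD) only.

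**The concern.** An endpoint needs a population at risk, a way of being observed, a threshold and an analysis that agree with one another. Here the endpoint belongs to an artery that has been stented, while the analysis sets and the clock are those of a stroke endpoint in all randomised patients. The imaging supports one reading per patient at a fixed time, while the endpoint's wording implies surveillance over the whole of follow-up. The only shell that could carry the result uses a different inequality and a denominator that need not consist of successfully stented arteries.

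At stake is the trial's statement about how durable stenting is. Two analysts following the SAP in good faith could report different quantities under the same name, and one of those quantities would be a between-arm comparison that cannot be interpreted.

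**Working it through.** The SAP states no restenosis rate, event count or power, so there is no figure to reproduce. The check sets the rules side by side and then illustrates one consequence.

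**1. Population.** Restenosis requires a treated artery. ITT keeps every randomised patient in the allocated arm. A medical-arm patient has no treated artery unless he or she crosses over, so most of that arm cannot have the event by definition. A difference or hazard ratio between arms then reflects the definition and not an effect of treatment. Per protocol does not rescue the comparison: its medical arm contains patients who received medical treatment alone.

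**2. Time.** The clock starts at randomisation, before any artery has been stented. With one scheduled follow-up scan, the event time is in effect the scan date. For the first recruits, follow-up continues for about 7.5 − 1 = 6.5 years after that scan with no scheduled imaging. A patient without a 1-year scan contributes event-free time in which restenosis was not looked for. The data support a proportion at 1 year, not a rate over follow-up.

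**3. Threshold.** Take a reading of exactly 50% in a stented artery at 1 year. Under the endpoint (more than 50%) it is not restenosis. In the imaging table (50% or more) it is counted.

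**4. What the by-arm figure contains.** In the stenting-arm row, a patient at 50% or more at 1 year may have (a) restenosis, (b) an original stenosis that was never stented, which section 3.3 foresees when it sets a 30-day start for patients allocated stenting in whom it was not performed, or (c) residual stenosis left by the procedure. Mean (SD) after stenting does not separate (a) from (c).

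*Illustration only; every input is an assumption.* Let
- u = share of the stenting arm not stented
- q = share of those still at 50% or more at 1 year
- s = share of stented patients with residual stenosis of 50% or more, assumed to persist
- r = true restenosis among the successfully stented

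The row then shows

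qu + (1 − u)[s + (1 − s)r].

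With q = 80%:

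| u | s | Row if r = 10% | Row if r = 20% |
|---|---|---|---|
| 0 | 0 | 10% | 20% |
| 0 | 5% | 14.5% | 24% |
| 10% | 0 | 17% | 26% |
| 20% | 0 | 24% | 32% |
| 40% | 0 | 38% | 44% |

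For example, u = 20%, s = 0 and r = 20% give 0.8 × 0.2 + 0.8 × 0.2 = 32%.

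With s = 0 the excess is u(q − r). It shrinks if fewer unstented patients stay at 50% or more, and it vanishes when q = r. With u = 0, as per protocol, the excess is s(1 − r): 0.05 × 0.8 = 4 percentage points in the second line at r = 20%. In this model the row is sure to equal the restenosis proportion only when u = 0 and s = 0.

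**The case against.** The best case for the plan is that it never names Cox regression for restenosis. Cox is conditional on sufficient events, the log-rank test is tied to stroke, and Table 3 has no restenosis row. The only follow-up imaging shell already gives 1-year proportions, and nothing in it claims to report restenosis. The imaging table carries no population label in the text available, so reading its rows as allocated arms is an inference from the ITT rule. The per-protocol set removes patients allocated stenting who were not stented.

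Much of this stands, and it limits the point. The Cox analysis follows only from the general wording of section 3.3. The missing row in Table 3 is weak evidence either way, since Table 3 also omits disabling stroke. If Cox was not intended, the SAP sets no method or denominator for this endpoint. The per-protocol set deals with unstented patients but not with residual stenosis or the lack of a treated artery in the medical arm.

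A reader might also infer more than the SAP supports:
- *That patients who die or miss the scan are counted as free of restenosis.* Section 3.3 censors at death and last contact, and no such imputation is stated.
- *That the endpoint is diluted by a calculable amount when spread over follow-up.* A rate per person-year and a 1-year proportion are different quantities, and setting one against the other does not show bias.
- *That the per-protocol criterion "Patients in whom central imaging review confirmed vertebral stenosis of ≥50" per cent contradicts the endpoint.* It is a criterion on the original stenosis and need not match a restenosis cut-off. The conflict that matters is with the imaging table.
- *That there is no other imaging.* Stenosis is also measured at baseline and at the stenting procedure. Only scheduled follow-up imaging is confined to 1 year.

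**Conclusion.** The point holds as a conflict between rules that the SAP itself states. An ITT between-arm or time-to-event analysis of restenosis is not meaningful, because the medical arm has no treated artery apart from cross-overs and there is one scheduled follow-up scan. The by-arm imaging figure can mix restenosis with residual stenosis and, under ITT, with stenosis that was never stented. Readings of exactly 50% are classed in two ways.

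The size of the error cannot be derived from the SAP, which gives no stented share, scan completeness, residual stenosis or restenosis rate. The table above shows direction and mechanism under assumed values and is not an estimate for this trial. The conclusion rests on two inferences: that the general wording on endpoints and follow-up covers restenosis, since no exception is made, and that the imaging table's rows follow the ITT grouping. One secondary endpoint is affected; the primary analysis is not.

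**What to change.** - Reconcile the threshold so that the endpoint and the imaging table use the same one, checking it against the protocol's definition.
- Report restenosis as a descriptive 1-year proportion with an exact 95% confidence interval. The denominator is patients who were stented, were below the threshold immediately after the procedure and have a readable 1-year scan. The post-procedure condition keeps residual stenosis from being counted as restenosis; the imaging table already provides for those readings.
- Show beside it the numbers not stented, with residual stenosis, dead before the scan and not scanned.
- Exempt restenosis explicitly from the ITT between-arm comparison and from the Cox analyses.
- Add a row for stented patients to the imaging table.

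The cost is a few lines in section 3.3 and one table row with its counts; no new scans are needed. The denominator becomes smaller and the interval wider. Restricting to scanned survivors may also introduce selection, which the added counts make visible but do not remove.

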# Statistical Analysis Plan (SAP) for Vertebral artery Ischaemia Stenting Trial (VIST)

# 1. SHORT DESCRIPTION OF PROJECT

Does vertebral artery stenting prevent recurrent stroke in symptomatic vertebral artery stenosis?

See VIST clinical study protocol Version 8.0 (10th June 2014) for details.

VIST is an international multicentre randomised controlled trial with the main aim to investigate the risks and benefits of vertebral angioplasty and stenting plus best medical treatment for symptomatic vertebral stenosis compared with best medical treatment alone. The efficacy is determined for the cohort as a whole and for extracranial and intracranial vertebral stenosis separately.

From an analytic point of view, we are treating VIST as a non-inferiority or equivalence trial, that is, a trial aimed to determine whether stenting is as good as best medical therapy alone in preventing recurrent stroke in patients with vertebral artery stenosis.

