#### 3.5. Sample size calculations

At trial initiation, we did power calculations using a power of 80% and two-sided significance level of 5%, and assuming that the risk of stroke in the medically treated arm would be 12% in year 1, 7% in years 2, and 5% in years 3 (i.e. 24% over a 3-year period). It was further assumed that the risk reduction in the stented arm would be 45% (including periprocedural rate). Based on these assumptions, the number of patients needed was estimated to be 490 (245 per arm). This number was increased by 10% to allow for stent failure, crossover, and loss to follow-up, thus giving a sample size of 540 patients. Because of early termination of the trial owing to low recruitment rate, the actual number of patients enrolled was 182.

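### Section 3.3 splits the main analyses by location of stroke where the rest of the SAP splits by location of stenosis, and no test compares the treatment effect between locations

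*SAP*

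**What the plan says.** The SAP describes the location analysis in four places.

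- Section 1 (aim): "The efficacy is determined for the cohort as a whole and for extracranial and intracranial vertebral stenosis separately".
- Section 3.3 (methods): "The main analyses will be repeated for intracranial and extracranial strokes separately".
- Table 3 in section 4: under the primary endpoint, the rows are "Extracranial vertebral artery target stenosis" and "Intracranial vertebral artery target stenosis", in a table with hazard ratio and P value columns.
- Table 1 in section 4: location of the target stenosis is a baseline characteristic, extracranial being V1 to V3 and intracranial V4.

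The 30-day table (Table 4) has bare extracranial and intracranial rows beneath posterior circulation stroke, which fit either definition.

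On testing, section 3.3 says: "Hypothesis tests will be 2-sided using a significance level of 0.05". For additional analyses, if events suffice, "we will adjust for centre and predefined risk factors". The factors are age, sex, body mass index and the vascular factors in Table 1. Location has its own heading in Table 1, outside the vascular risk factors. No interaction or heterogeneity test by location appears anywhere in the SAP.

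**The concern.** There are two linked problems.

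The first is the definition. Location of the target stenosis is fixed before randomisation and divides all 182 patients into two groups, each with a randomised comparison. Location of a stroke is known only for patients who have one, and only afterwards. Splitting on it gives two different endpoints in the whole cohort, not two groups of patients. The SAP does not define an extracranial stroke, and the term does not describe a usable category.

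The second is inference. The plan yields one P value for extracranial and one for intracranial disease. Readers will set them side by side. If one is below 0.05 and the other is not, the natural conclusion is that stenting works at one site and not at the other. Two separate tests do not support that conclusion; a direct comparison of the two effects is needed. In a trial that stopped at about a third of its target (182 of 540), the risk of this misreading is large.

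**Working it through.** **Definition.** Section 1, Table 1 and Table 3 all use the stenosis. Only the sentence in section 3.3 uses the stroke. The contradiction is between that sentence and the rest.

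**Inputs, all from SAP section 3.5.** Control 3-year stroke risk 24%; 45% reduction, so 0.24 × 0.55 = 13.2% with stenting; "using a power of 80% and two-sided significance level of 5"%; 490 patients before inflation; 182 enrolled. The split by location is not stated, so it is assumed at 50:50 to 85:15.

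**The plan's own figure.** The SAP does not name its formula. Freedman's formula with HR 0.55 needs (1.96 + 0.842)² × (1.55/0.45)² = 93.1, so 94 events. The mean 3-year risk is (0.24 + 1 − 0.76^0.55)/2 = (0.240 + 0.140)/2 = 0.190, and 94/0.190 = 495, within about 1% of 490. The figure is reproduced. It is for the whole cohort; none is given for a location or an interaction.

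**Expected strokes at 182 patients.** 182 × (0.24 + 0.132)/2 = 33.9, if the 3-year risks apply.

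**Power per location, comparing proportions.** With n per arm and p̄ = 0.186, power = Φ{[0.108√n − 1.96√(2 × 0.186 × 0.814)] / √(0.24 × 0.76 + 0.132 × 0.868)}. For the whole cohort (n = 91) this is 46%.

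**Chance that exactly one location reaches p<0.05 when the true effect is the same in both.** a(1 − b) + b(1 − a), where a and b are the two powers.

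**Power of the interaction test.** This takes the planned effect in the larger location and none in the smaller. The log hazard ratio is that of HR = ln(0.868)/ln(0.76) = 0.516, and SE = √(sum of 1/events over the four arm-by-location cells). At 50:50 the cells hold 10.9, 6.0, 10.9 and 10.9 events, so SE = 0.664 and power = 17%.

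| Assumed split | Patients | Expected strokes | Power, larger / smaller | Exactly one p<0.05 | Interaction power |
|---|---|---|---|---|---|
| 50:50 | 91 / 91 | 17 / 17 | 26% / 26% | 39% | 17% |
| 60:40 | 109 / 73 | 20 / 14 | 30% / 22% | 39% | 17% |
| 70:30 | 127 / 55 | 24 / 10 | 35% / 17% | 40% | 16% |
| 80:20 | 146 / 36 | 27 / 7 | 39% / 13% | 42% | 13% |
| 85:15 | 155 / 27 | 29 / 5 | 41% / 11% | 43% | 12% |

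**Cross-check on the hazard ratio scale.** With HR 0.55 and e events in a location, power = Φ(0.598√e/2 − 1.96). It is 23% at e = 17, 31% at 24 and 16% at 10. The chance of exactly one significant location is then 36% at 17/17, 37% at 24/10 and 39% at 29/5. The two methods together give 36% to 43%.

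**Width of the intervals.** For one location the 95% limits are the HR divided and multiplied by exp(1.96 × 2/√e): a factor of 2.2 at 24 events and 3.5 at 10. For the ratio of the two HRs the factor is exp(1.96√(4/e₁ + 4/e₂)): 3.8 at 17/17, 4.4 at 24/10 and 6.7 at 29/5.

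**Sensitivity to the event count.** Follow-up runs from 1 to about 7.5 years (section 3.3), so 34 is only a guide. With half or twice as many strokes, evenly split (8.5 or 34 per location), the hazard-ratio formula gives 14% or 41% power, and 2a(1 − a) = 24% or 49% for exactly one significant location.

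**The case against.** The strongest defence is that the intended meaning is plain. Three places point to the stenosis and one to the stroke, and an analyst is unlikely to carry out a split that has no usable extracranial category. That stands. A reader might infer from section 3.3 that the SAP as a whole defines the analysis by where the stroke occurs; section 1, Table 1 and Table 3 do not support this.

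It can also be said that section 1 asks for efficacy in each location, so location-specific estimates are what the aim requires. That stands too. A reader might go further and infer that the interaction is the trial's main question; the SAP does not say so. The estimates should stay. What is missing is the comparison that guards against misreading them.

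Third, an interaction test at this sample size would usually be non-significant even if a real difference existed. That is correct, and it must be disclosed. It also means that the data cannot separate the locations well: an interval of a factor of about 4 or more either way shows this openly, and two P values hide it.

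Two further readings are tempting. One is to size the problem by the 1 − 0.95² = 9.75% chance of at least one false positive across two independent tests. That figure measures multiplicity, not the missing comparison. The other is that the whole-cohort log-rank test and Cox model are wrong unless stratified by location. Nothing in the SAP says that randomisation was stratified by location, and an unstratified test is valid in a randomised comparison, so stratifying would be a preference.

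**Conclusion.** The point holds in two parts. Section 3.3 contradicts section 1 and Table 3 on what defines the location split. This is probably a slip in one sentence, but in operative methods text, and it must be reconciled. Separately, the SAP plans location-specific hazard ratios with P values and no test of whether the effect differs. On the plan's own rates, each location has roughly 11% to 41% power, and identical true effects would give one significant and one non-significant location about 36% to 43% of the time. These figures assume about 34 strokes and a split between 50:50 and 85:15; neither the realised count nor the split is in the SAP. The contradiction and the absent test do not depend on those assumptions.

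**What to change.** 1. In section 3.3, replace the reference to strokes with target stenosis location at randomisation (V1 to V3 versus V4), and label the location rows of Table 4 in the same way.
2. Estimate both location-specific hazard ratios, with 95% confidence intervals, from one Cox model containing treatment, location and their product.
3. Add the interaction estimate to Table 3 as a ratio of hazard ratios, with its confidence interval and P value.
4. State that a difference between locations will not be inferred from one significant and one non-significant result, and that the location results are exploratory.

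The cost is one phrase, one model term and one table line. Location is already collected for Table 1, and no stated figure changes. The drawback is the interaction test's power of about 12% to 17%: a non-significant result will not show that the effects are alike, so it should be read through its wide interval. If the split is very uneven, the smaller location may hold only about five strokes. The event counts by arm should then be shown beside the estimates, in keeping with the SAP's condition that Cox models are fitted only if events suffice.
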